e)	Imaging evidence of traumatic head injury
2.	Associated, immediately following the head injury, with at least one:
a)	Transient confusion, disorientation or impaired consciousness
b)	Loss of memory for events immediately before or after injury
c)	Two or more of: nausea, vomiting, visual disturbance, dizziness/vertigo, impaired memory/concentration, gait instability
C.	Headache is reported to have developed within 7 days after one of:
1.	The injury to the head
2.	Regaining consciousness following injury to the head
3.	Discontinuation of medication(s) that impair the ability to sense or report headache following injury to the head
D.	If headache persists for >3 months following onset then it is "persistent" PTH. If headache resolved within 3 months of onset or 3 months have not yet passed, then it is "acute" PTH.
E.	Not better accounted for by another ICHD-3 diagnosis

- PTH onset 7- 56 days prior to the time of enrollment
- Adults 18-70 years of age
- Willing to receive erenumab treatment
- Willing to maintain a headache diary
- Willing and able to return for follow-up visits

Additional Inclusion Criteria for the Clinical Trial (assessed after run-in phase)

- 4 or more moderate or severe headache days during the 4-week run-in phase

- An increase of at least 2 moderate to severe headache days compared to pre-TBI
- At least a 30% increase in moderate to severe headache days compared to pre-TBI
- At least 80% compliant with diary keeping during the 4-week run-in phase (i.e. provides data on at least 80% of days)

Exclusion Criteria

- Chronic headache (i.e. at least 15 headache days/month for more than 3 months) within 12 months prior to the mTBI that led to the current PTH, including PPTH, chronic migraine, medication overuse headache, new daily persistent headache, hemicrania continua, chronic tension-type headache.
- Diminished decision-making capacity that in the investigator's opinion would interfere with the person's ability to provide informed consent and complete study procedures
- Started or changed dose of a headache preventive medication within the 3 months prior to screening.
- Use of onabotulinumtoxinA in the head, neck or face region within 6 months of screening
- During the 6 months before screening, use of opioids or barbiturates on an average of at least 4 days per month

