
during the open label extension were similar to that observed in the double-blind phase and comparable to placebo.

Hypothesis/Objective

The objective of this study is to collect hypothesis generating data about whether intervention with erenumab is an effective treatment for PTH attributed to mTBI. Participants will receive erenumab when PTH has been present for 35-84 days. Once PTH has been persistent for this period of time, patients may be less likely to remit or improve spontaneously compared to if they were enrolled earlier after PTH onset. Thus, this population of individuals with PTH would be considered in high need of treatment.

Specific Aims/Study Endpoints

Primary endpoint

- Moderate-to-severe headache day frequency measured at weeks 9-12 after administration of first dose of erenumab 140mg vs. frequency of moderate-to-severe headache days during the 4-week baseline phase (BP). A moderate-to-severe headache day is defined as any headache lasting at least 2 hours and which at any point reaches at least moderate intensity.

Secondary endpoints

- Percentage of patients with at least a 50% reduction in headache days during weeks 9-12 after administration of first dose of erenumab 140 mg compared to BP.
- Percentage of patients with chronic headache defined as ≥ 15 headache days during weeks 9-12 after administration of first dose of erenumab 140mg compared to BP.
- Headache Impact Test (HIT-6) at weeks 9-12 after administration of first dose of erenumab 140 mg compared to BP.
- Acute treatment day frequency measured at weeks 9-12 after administration of first dose of erenumab 140mg compared to BP. (Acute treatment day is any day on which an analgesic, triptan, or ergotamine containing medication is taken, or device neuromodulation [e.g. vagal or trigeminal nerve electrical stimulation or single pulse transcranial magnetic stimulation] is administered to relieve headache)

Methods

This is a phase II prospective, open-label clinical trial of a CGRP receptor mAb for treatment of PTH. Of note, this was originally designed as a randomized, placebo-controlled clinical trial. However, recruitment into the clinical trial was slow. Since the estimated total enrollment would

be inadequate for making comparisons between the placebo and erenumab groups, the study was revised to an open-label design.

[figure not shown]

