Individuals with PTH will be receive monthly subcutaneous administration of erenumab 140 mg over a 3-month period (total of 3 injections). The primary endpoint will be the mean number of moderate-to-severe headache days between 9-12 weeks after treatment vs. the number of moderate-to-severe headache days during the 4-week BP. Subjects will maintain an electronic daily diary during the 4-week BP, for the 12 weeks post-first treatment, and during weeks 21-24 post-first treatment.

All participants in this clinical trial will complete baseline and follow-up questionnaires described in detail in the separate human studies protocol subtitled "Individual Projects Excluding Clinical Trial" within the "Phenotyping and Neurophysiology" section. In brief, the following questionnaires will be used to collect baseline and follow-up data:

- 1) TBI and PTH characteristics
- 2) Post-TBI symptoms using the 22-item Symptom Evaluation Checklist from the Sport Concussion Assessment Tool (SCAT)
- 3) Headache Impact Test (HIT-6)
- 4) Self-Rating Questionnaire on Hypersensitivity to Sound
- 5) Photosensitivity Assessment Questionnaire
- 6) Allodynia Symptom Checklist (ASC-12)
- 7) State Trait Anxiety Inventory (STAI)
- 8) Beck Depression Inventory (BDI)
- 9) Posttraumatic Stress Disorder Checklist
- 10) Survey of Autonomic Symptoms
- 11) Pain Catastrophizing Questionnaire
- 12) Insomnia Severity Index
- 13) Cognitive Function
- 14) Dizziness Handicap Inventory
- 15) Trail Making Test A and B
- 16) Controlled Oral Word Association Test (COWAT)
- 17) Global Impression of Change
- 18) Follow-up Headache Characteristics
- 19) Adverse Events
- 20) Sensory Testing Results *not applicable for Rochester and Florida sites
- 21) Vital Signs
- 22) Pregnancy Test Results

In addition, all research participants will maintain a daily electronic headache and symptom diary to provide data on headaches, treatment, and presence and severity of associated symptoms. The diary will be maintained for the first 4 weeks, starting with enrollment (i.e. first research visit) and through week 16 (i.e. third research visit), and again during weeks 21-24 post-first treatment. The electronic diary requires individuals to record whether they did or did not have a headache each day, the severity of their pain, headache duration, level of functional disability due to the headache, and use of medication. To optimize compliance with diary maintenance, the amount of

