time required to complete the daily entries has been minimized to less than 2 minutes. Subjects are asked to complete their headache diary at the end of each day. Data from the headache and symptom diary will be used to assess changes in symptoms over time, to prospectively determine who has persistence vs. resolution of PTH, to determine enrollment in the clinical trial depending on PTH persistence and frequency of moderate to severe headache days, and to track response to treatment for those individuals enrolled into the clinical trial.

Stratification, Randomization and Masking: This is an open-label study in which there is no stratification, randomization, or masking.

All study drugs will be prepared by a Mayo Clinic pharmacist who has no other role in the study. The drug will be delivered by pharmacy staff to the enrolling investigator clinician or research nurse, who will be responsible for delivering the injection. There will be strict adherence to inclusion and exclusion criteria. Participants will receive instructions and training from a study coordinator on how to use the electronic diary for daily reporting of headaches. A urine pregnancy test will be required for female participants prior to each of the erenumab treatments. Throughout the study, participants will record data in the daily diary for the previous 24 h period.

Treatment with Erenumab: Patients receive treatment with 140 mg of erenumab via subcutaneous injection. Treatment will be administered under research team observation. Injections will be administered using two 70 mg/1 mL prefilled syringes in the abdomen (except for a two-inch area right around the navel), thigh, or outer area of upper arm according to patient preference. If using the same body site for the two separate injections, the second injection is not to be given at the same spot used for the first injection.

Erenumab will be stored refrigerated at 2°C to 8°C (36°F to 46°F) until time of use. Once removed from the refrigerator, it will be kept at room temperature and used within 7 days. Prior to administration, erenumab will sit at room temperature for at least 30 minutes, protected from direct sunlight.

Concomitant Therapy

There are no restrictions on the use of as needed headache/pain therapies. Patients will record their use of such therapies within the headache diary and these data will be used when measuring patient outcomes.

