For patients who are participating in the clinical trial, no preventive therapy for headache should be started. Preventive therapies include drugs, biologics, devices, procedures, and non-pharmacological modalities.

Statistical Plan:

Sample Size- all individuals who qualify for the clinical trial and are interested in participating will be enrolled, up to a maximum of 112 participants. This sample size is empirical and results will be used for hypothesis generation.

Headache Diary - Values for missing calendar day entries in a given month will be imputed by prorating scores of 4-week post-treatment periods with 20–27 days of diary data. For months with less than 10 days of diary data, scores will be estimated by the substitution of the patient's previous 28-day period mean score, multiplied by the ratio of the mean for all patients in the same period and divided by the mean for all patients in the previous period. For post-treatment periods with 10–19 days of diary data, scores were estimated using a mean of both methods.

Outcomes - Efficacy analyses will be conducted in the full analysis set, which includes all subjects (intent-to-treat population) who received at least one dose of study drug and have at least 10 days of efficacy assessments for the primary endpoint measured during weeks 9–12. Safety analyses will be performed in all subjects who receive at least one dose of study drug. The primary and secondary endpoints will be analyzed using a within-person one-sample t-test. Signed rank test will be used for the primary analysis if there is a deviation from normality assumption as assessed by Shapiro Wilk's test. Confidence intervals will be calculated. SAS version 9.4 (SAS Institute, Cary NC) will be used for all statistical analyses.

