IRB Approvals and Informed Consent: IRB approvals will be obtained from the Mayo Clinic IRB, the Phoenix VA IRB and the DOD HRPO prior to starting any human study research. Written informed consent will be obtained from all subjects prior to their participation. The informed consent process will be based upon the Declaration of Helsinki principles and in accordance with US 21CFR. Applicable HIPAA privacy notifications will be included. Participants will be given ample time and opportunities to ask questions about this study. All consent forms will require IRB approval prior to their use. Patients will be informed of their right to withdraw from the study at any time. Enrolling clinicians will be made aware that the needs of their patients come first and thus the safety and wellbeing of study participants is of primary concern. The study will be done in accordance with the principles of Good Clinical Practice and with US Food and Drug Administration (FDA) and International Committee for Harmonization guidelines for safety

monitoring. Consent documents will be stored for a minimum of 3 years after conclusion of the study. The research participant will retain a copy of their signed consent document.

Study Materials: Study drug will be provided by Amgen, Inc, the manufacturer of erenumab.

Participant Compensation

Participants will be compensated \$50 per research visit and \$35 per month for headache diary completion at least 80% of the time for a total of up to \$175.

Adverse Events

An adverse event is defined as any untoward medical occurrence in a clinical trial patient. The event does not necessarily have a causal relationship with study treatment. The investigator is responsible for ensuring that any adverse events observed by the investigator or reported by the subject are recorded in the patient's record. The definition of adverse events includes worsening of a pre-existing medical condition. Worsening indicates that the pre-existing medical condition or underlying disease has increased in severity, frequency, and/or duration more than would be expected, and/or has an association with a significantly worse outcome than expected. A pre-existing condition that has not worsened more than anticipated during the study or involves an intervention such as elective cosmetic surgery or a medical procedure while on study is not considered an adverse event.

Definition of Serious Adverse Events

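### The efficacy set is called intent-to-treat but requires 10 assessment days in weeks 9–12, and no efficacy analysis of all dosed patients is named

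*Combined protocol and SAP*

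**What the plan says.** **Efficacy set.** Statistical Plan, Outcomes: efficacy is analysed in "all subjects (intent-to-treat population) who received at least one dose of study drug and have at least 10 days of efficacy assessments". The days that count are those contributing to the primary endpoint in weeks 9–12.

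**Safety set.** The next sentence gives the only set of all dosed patients: "Safety analyses will be performed in all subjects who receive at least one dose of study drug".

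**Endpoints.** Specific Aims/Study Endpoints lists one primary and four secondary endpoints, all measured in weeks 9–12 against the baseline phase. Two are percentages (50% responders, chronic headache). One is "Headache Impact Test (HIT-6) at weeks 9-12 after administration of first dose of erenumab 140 mg compared to BP"; Methods lists HIT-6 among the questionnaires, not as a diary item.

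**Diary.** Methods: "Subjects will maintain an electronic daily diary during the 4-week BP, for the 12 weeks post-first treatment". Diary data therefore exist for weeks 1–8 as well. Entry requires "At least 80% compliant with diary keeping during the 4-week run-in phase".

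**Missing days.** Statistical Plan, Headache Diary, has three rules: prorating for 20–27 days; for fewer than 10 days, the previous period's score scaled by a ratio of period means; and the average of both methods for 10–19 days.

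**Purpose.** Statistical Plan, Sample Size, sets a maximum of 112 and adds: "This sample size is empirical and results will be used for hypothesis generation". The trial is open-label with no randomization.

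**The concern.** A set that requires outcome-window data selects patients on what happened after treatment began. Calling it intent-to-treat tells a reader of the results that nobody was dropped for that reason, which is not so.

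Selective loss is plausible in either direction. Participants may withdraw at any time, and no headache preventive should be started during the trial, so a patient who is not improving may leave. A patient who has recovered may simply stop filling in the diary. With no comparator arm, neither effect would show up as an imbalance.

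The plan asks for neither a count nor a description of the excluded patients, although their baseline diary and any weeks 1–8 data will be on file. At stake is the estimate carried forward to a later trial: its reader should know whether it describes everyone treated or only those who kept recording.

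**Working it through.** The plan states no dropout rate, effect size or standard deviation, and 112 is given without a derivation, so there is no figure to reproduce.

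**1. Who is excluded.** Weeks 9–12 are days 57–84 after the first dose. A complete diary that stops on day 65 gives 65 − 56 = 9 days (excluded); one that stops on day 66 gives 10 (kept). Because all five endpoints use this set and window, exclusion removes the patient from all five. A patient with a HIT-6 score in the window but nine diary days is dropped from HIT-6 too.

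**2. The under-10-day rule.** It applies when a period has fewer than 10 days. The set admits only patients with 10 or more days in weeks 9–12. The two conditions cannot both hold in that window, so the rule never scores it for an analysed patient. It can still score other periods, such as weeks 1–4 or 5–8, but no listed endpoint uses those. Baseline does not need it: 0.8 × 28 = 22.4, so entrants have at least 23 baseline days.

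**3. Illustration for percentages (assumed inputs).** Let q be the fraction of dosed patients excluded and p the rate in the efficacy set. The all-dosed rate lies between p(1 − q) and p(1 − q) + q. I take p = 50% for responders (the protocol's Background cites 50% for 140 mg in an episodic migraine trial; it is used here only as an example) and p = 20% for chronic headache.

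| q | Excluded of 112 | Responders, all dosed | Chronic, all dosed |
|---|---|---|---|
| 10% | 11 | 45–55% | 18–28% |
| 20% | 22 | 40–60% | 16–36% |
| 30% | 34 | 35–65% | 14–44% |

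For scale, with 101, 90 or 78 patients left, the 95% half-width at a 50% rate is 1.96 × √(0.25/n) = 9.8, 10.3 or 11.1 points, against a missing-data half-range (q/2) of 5, 10 or 15 points.

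**4. Illustration for mean change (assumed −4.0 days in the efficacy set).** With d the mean change in excluded patients, the all-dosed mean is (1 − q)(−4.0) + q·d.

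| d (assumed) | q = 10% | q = 20% | q = 30% |
|---|---|---|---|
| +2 (worsened) | −3.4 | −2.8 | −2.2 |
| 0 (no change) | −3.6 | −3.2 | −2.8 |
| −4 (same as others) | −4.0 | −4.0 | −4.0 |
| −8 (needs mean baseline of at least 8 days) | −4.4 | −4.8 | −5.2 |

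**5. No single method corrects this.** Assume evaluable period means of 10, 7, 6.5 and 6 days (baseline, then weeks 1–4, 5–8, 9–12), and that 20% are excluded, also with baseline 10.
- If the excluded truly stayed at 10, the all-dosed change is 0.8 × (−4) + 0.2 × 0 = −3.2.
- For loss straight after the first dose, a missing-at-random model sees the same baseline, predicts 6, and gives −4.0.
- For loss after week 8, with AR(1) correlation 0.7, it predicts 6 + 0.7 × (10 − 6.5) = 8.45, a change of −1.55, so 0.8 × (−4) + 0.2 × (−1.55) = −3.5. With compound-symmetric correlation 0.5 the weights are 0.5/(1 + 2 × 0.5) = 0.25, the prediction is 6 + 0.25 × (0 + 3 + 3.5) = 7.625, and the result is −3.7.
- If the excluded truly matched the others (−4.0), assigning no change gives −3.2 and is the analysis in error.

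Each analysis is right only under its own assumption.

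**The case against.** **The case for leaving the plan alone.** There is no randomized comparison for intent-to-treat to protect, no confirmatory decision depends on the result, and the 10-day condition stands in the same sentence as the label. The label may be meant to gloss only the first words of that sentence. Loss may also be small: diary compliance is screened at run-in, participants are paid "per month for headache diary completion at least 80% of the time", and Patient Retention provides for immediate contact on non-compliance.

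**What stands.** All of this lowers the weight of the point. It does not remove it. However the parenthesis is read, the set analysed is not the population named. The safeguards reduce loss but do not count it or examine its effect.

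**Stronger readings that the documents do not support.**
- *The result will be biased in favour of erenumab.* Section 4 of the working shows shifts in both directions, and nothing in the documents says which applies.
- *Methods contradicts the set by saying the diary serves "to track response to treatment for those individuals enrolled into the clinical trial".* That sentence gives a reason for collecting diary data; it defines no analysis set.
- *The rule is perverse because a patient with 93 of 112 diary days (28 + 65) can be excluded while one with 33 (23 + 10) is kept.* Total diary days do not measure information in the endpoint window, where these patients have 9 and 10 days.
- *The under-10-day rule is itself an error.* It can still score other periods. Its scope is simply not stated.
- *Exclusion matters only above about 21%.* That is where the half-range meets sampling error for a 50% rate at 112 patients. At an assumed 60 or 40 patients it is about 30% or 40%, and for the upper limit of a 20% chronic rate at 112 patients about 10%.

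**Conclusion.** The point holds. The efficacy set is mislabelled: it selects on post-dose data in the outcome window and takes HIT-6 and both percentage denominators with it. The plan names no efficacy analysis of all dosed patients, and the under-10-day rule and the set definition need reconciling.

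The size and direction of any bias cannot be established from the documents. The ranges in the working rest on assumed exclusion of 10–30% and assumed rates and changes; they show sensitivity and do not predict the result. At 10% exclusion the responder half-range is well inside sampling error at the maximum sample size; at 30% it is larger.

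This should be fixed before the analysis, but because the trial is single-arm and hypothesis-generating and the restriction is disclosed, it is at the lower end of what warrants a change.

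**What to change.** 1. Drop the intent-to-treat label and call the 10-day set evaluable. Keep the planned tests in it. Report how many dosed patients are excluded, why, and their baseline and available weeks 1–8 data.
2. Analyse HIT-6 in every dosed patient who has the questionnaire, whatever the diary count.
3. Add an all-dosed sensitivity analysis with its missing-data assumption stated. For the primary endpoint, fit a repeated-measures model to all collected diary data (saying how periods with few days enter it) and, beside it, assign no change from baseline to those under 10 days. Present the two as a range and not as a correction. For the two percentage endpoints, put all dosed patients in the denominator and count those under 10 days each way.
4. State which periods the under-10-day imputation rule applies to, so that it agrees with the set definition.

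**Cost.** Wording changes and a little more analysis of data already being collected; no new visits or patients. The all-dosed estimate may be less favourable and less precise than the evaluable one, and readers get a range in place of a single number.

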Erenumab is a CGRP receptor mAb that has been demonstrated in phase 2 and phase 3 studies to be effective, safe, and well tolerated for the preventive treatment of episodic (< 15 headache days per month) and chronic migraine (\geq 15 headache days per month). Erenumab received FDA approval for the prevention of migraine in May 2018. In a phase 3 placebo-controlled trial in subjects with episodic migraine (STRIVE), 955 patients were randomized to receive monthly subcutaneous injections of erenumab 70mg, erenumab 140mg, or placebo over 6 months.⁷⁷ The primary endpoint (mean monthly migraine days; MMDs) and all secondary endpoints were achieved. The responder rates (> 50% reduction in MMDs) to erenumab 70mg (43%) and 140mg (50%) were superior to placebo (27%; $p<0.001$). Adverse events were experienced by 64% in the placebo group vs. 57% and 56% in the 70mg/140mg groups respectively. There were no treatment-related serious adverse events in either erenumab group. In another phase 3 randomized, double-blind, placebo-controlled study to evaluate the efficacy and safety of erenumab 70mg in episodic migraine prevention (ARISE), 577 adults were randomized to subcutaneous, monthly placebo, or erenumab (70mg).⁷⁶ Erenumab significantly reduced MMD (primary endpoint) at weeks 9-12. A \geq 50% reduction in MMDs was achieved by 40% and 30% in erenumab 70mg and placebo groups (odds ratio: 1.6; $p=0.010$). Erenumab-treated subjects also experienced a significant reduction in monthly use of acute migraine-specific medications compared to placebo ($p=0.002$). Similar to STRIVE, erenumab 70mg was well tolerated, and there were no treatment-related serious adverse events. In a recently conducted randomized, double-blind, placebo-controlled study to evaluate the efficacy and safety of erenumab 70mg and 140mg for the preventive treatment of chronic migraine, 667 patients were randomized to receive monthly subcutaneous injections over a 3-month period.⁸⁵ Erenumab was demonstrated to be superior for the primary endpoint of MMD reduction at weeks 9-12. Responder rates were also superior for erenumab 70mg (40%; $p<0.001$) and 140mg (40%; $p<0.001$) compared to placebo (24%). Similar to the episodic migraine trials, erenumab was demonstrated to be well tolerated, with an adverse event profile similar to placebo. In a long-term open-label extension study (total exposure of 555.4 patient-years), the safety and tolerability of erenumab was similar to that in the double-blind phase (25.9 and 34.1 patient-years for erenumab 70 mg and placebo, respectively).⁸⁶ At week 64, 65%, 42% and 26% of patients had response of \geq 50%, \geq 75% or 100%. Erenumab resulted in durable, clinically meaningful improvements across measures of disability, headache impact, and migraine-specific quality of life. Anti-AMG 334 antibodies occurred in 2.4% of the study population, but in all were transient except in one. Anti-AMG 334 antibodies did not impact efficacy or safety. With erenumab exposure of more than 2 years, safety and tolerability profiles

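### The 50% responder endpoint is assigned a within-person one-sample t-test with no stated null; against the natural null of 0%, the p-value says nothing about benefit

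*Combined protocol and SAP*

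**What the plan says.** The Outcomes paragraph of the Statistical Plan gives one method for everything: "The primary and secondary endpoints will be analyzed using a within-person one-sample t-test". It adds a signed rank alternative, for the primary analysis only, and says that confidence intervals will be calculated, without naming a method or level.

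Two of the four secondary endpoints, listed under Specific Aims/Study Endpoints, are percentages of patients. One is the responder endpoint: "Percentage of patients with at least a 50% reduction in headache days during weeks 9-12", measured against the baseline phase. The other is the chronic-headache endpoint: "Percentage of patients with chronic headache defined as" 15 or more headache days in weeks 9-12, also compared with baseline.

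The plan states no null value, reference rate, alpha or success threshold for the responder endpoint, and names no method for binary data. The Methods section says that "recruitment into the clinical trial was slow" and that the trial was therefore changed from a placebo-controlled to an open-label design. The Sample Size paragraph allows enrolment "up to a maximum of 112 participants" and adds: "This sample size is empirical and results will be used for hypothesis generation".

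**The concern.** A within-person test compares two values from the same patient, and its null is that the mean difference is zero. That works for headache days, HIT-6 and acute treatment days. It does not work for responder status: the 50% reduction is itself the change from baseline, so a patient has no baseline responder status to subtract.

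All that is left is a one-sample test of a 0/1 variable against some fixed number. As the plan gives none, the natural reading is zero. A true responder rate of 0% allows no responders at all, so a single one refutes it. Rejecting that null shows only that somebody improved by half. It does not separate a drug effect from spontaneous recovery, regression to the mean after selection on run-in frequency, or placebo response. In a single-arm open-label study, a small p-value beside a responder rate could nevertheless be taken as a sign of efficacy.

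**Working it through.** The plan has no figure to reproduce here. The check is to apply the stated rule to a 0/1 variable and see what it does.

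**Inputs.**
- Test: one-sample t-test, from the Outcomes paragraph.
- Null: 0%, inferred; the plan does not state it.
- Level: two-sided 0.05, assumed; the plan states none.
- Sample size: 112 is the ceiling. The realised number is unknown and recruitment was slow, so n = 20, 30 and 50 are also shown, as assumptions.
- Illustrative rates: the Background cites placebo 50% responder rates in migraine of 24%, 27% and 30%. For the 30% figure it says: "50% reduction in MMDs was achieved by 40% and 30% in erenumab 70mg and placebo groups". The plan does not adopt any of these as a benchmark.

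**Step 1: how many responders give p<0.05.** With k responders among n, the mean is k/n and the sample variance is k(n−k)/(n(n−1)). Testing against zero therefore gives t = √[k(n−1)/(n−k)] on n−1 degrees of freedom.

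| n | k = 3: p | k = 4: t | k = 4: p |
|---|---|---|---|
| 20 | 0.083 | √(4×19/16) = 2.179 | 0.042 |
| 30 | 0.083 | √(4×29/26) = 2.112 | 0.043 |
| 50 | 0.083 | √(4×49/46) = 2.064 | 0.044 |
| 112 | 0.083 | √(4×111/108) = 2.028 | 0.045 |

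Four is the smallest significant count at every n from 20 to 112. At n = 112 that is 4/112 = 3.6% (exact 95% interval 1.0% to 8.9%). With k = 1, t = 1 whatever n is, and p is 0.32 to 0.33. So the test also fails to reject with one, two or three responders, although the first has already disproved the null.

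**Step 2: how often it rejects when the rate is no better than a migraine placebo rate.** This is P(X ≥ 4) for X ~ Binomial(n, rate).

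| True rate | n = 20 | n = 30 | n = 50 |
|---|---|---|---|
| 24% | 74.3% | 95.2% | 99.92% |
| 30% | 89.3% | 99.1% | >99.99% |

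**Step 3: how often it rejects if no patient's underlying rate changes.** Let X1 (baseline) and X2 (weeks 9-12) be independent Binomial(28, mean/28). The chance of being a responder is P(X2 ≤ X1/2 | X1 ≥ 4).

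| Mean headache days per 28 | Responder chance | Rejects, n = 30 | Rejects, n = 50 |
|---|---|---|---|
| 6 | 14.3% | 64% | 94% |
| 8 | 7.9% | 21% | 57% |
| 10 | 4.5% | 4% | 18% |
| 14 | 1.1% | <1% | 0.2% |

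The documents give no baseline frequency, so this range does not fix a size; it shows that the rejection rate under no change is not controlled at any known level, and it can be below 5%. The model is also rough. The entry rule of four days counts moderate or severe headache days, whereas the responder endpoint counts headache days, which may be more numerous and would lower these figures. Treating days as independent and patients as alike may err the other way.

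**Step 4: intervals.** The t-based interval is k/n ± t(0.975, n−1) × s/√n.
- 20/50: 0.400 ± 2.010 × 0.0700 gives 25.9% to 54.1%; the exact interval is 26.4% to 54.8%. They nearly agree.
- 3/30: 0.100 ± 2.045 × 0.0557 gives −1.4% to 21.4%, which includes impossible values; exact is 2.1% to 26.5%, Wilson 3.5% to 25.6%.

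**The case against.** The 0% null is inferred, not written. Because the test sentence cannot literally apply to a variable with no baseline counterpart, it may be a loose blanket sentence meant for the endpoints it suits, with the responder percentage simply reported with its planned interval. The plan states no alpha or success criterion, calls its results hypothesis-generating, and does not say that the interval will be t-based. No before-after p-value in this design isolates a drug effect, so part of the harm is not specific to this endpoint. The no-change figures range too widely to establish a size.

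Most of this limits the harm, and it is why the point is minor. The no-change figures do not carry the conclusion. The interval problem is small at middle rates. But the sentence as written does cover every secondary endpoint, and nothing elsewhere supplies a null, a binary method or a fallback for this one. If another null is intended, the plan must state it. Headache-day or HIT-6 differences at least have a meaningful no-change null; here the inferred null is trivial, and a larger sample does not cure that.

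**Conclusion.** Wrong as written, and minor. The prescribed test does not fit the 50% responder endpoint, and its p-value cannot be read as evidence of benefit. The threshold of four responders at any n from 20 to 112 rests on the inferred 0% null and an assumed two-sided 0.05. The 74% to over 99.9% rejection probabilities also borrow migraine placebo rates, which only show scale, since the documents give no reference rate for post-traumatic headache. The lack of a stated null and of a method for a proportion rests on no assumption. The primary analysis is unaffected.

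**What to change.** Take the 50% responder endpoint out of the t-test sentence. State instead that it will be reported as n/N and a proportion with a 95% confidence interval, name the method (Clopper-Pearson exact, or Wilson), and drop any test against zero.

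This does not endorse the t-test for all the other secondary endpoints. The chronic-headache endpoint is binary too. It has a baseline value, so a no-change null is meaningful, but a paired binary method such as McNemar's test would suit it better.

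The cost is one sentence in the Statistical Plan and a standard PROC FREQ option in the SAS software already named. The only loss is a p-value that could not be interpreted as benefit.
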